There has been growing interest in the use of long-acting local anesthetics for improving pain control in orthopaedics⁷, particularly in the elective total joint arthroplasty population⁸. Studies have shown that arthroplasty patients receiving long-acting local anesthetics have decreased opiate requirements, reduced length of stay, and lower costs⁸⁻¹². Although well-demonstrated in the elective arthroplasty population, the effects of long-acting local anesthetics have yet to be demonstrated in the hip fracture population. Given that these fractures frequently occur in medically frail patients with multiple comorbidities^{13,14}, in whom post-operative confusion and delirium are relatively common^{15,16}, there is the potential for treatments that decrease opiate requirements to demonstrate substantial medical and economic benefits.

Exparel (liposomal bupivacaine) and long-acting local anesthetics have been used extensively in hip replacement surgery and have not been shown to be associated with any increased risks¹⁷⁻²³. In the case of patients with displaced femoral neck fractures treated with arthroplasty, the surgical techniques are identical to those being used in this study. Exparel has also been used in trauma surgery²⁴ as well as foot and ankle surgery²⁵ without any increased described risks, although its use explicitly in hip fractures has not been published. However, the PI has trained in other medical centers where Exparel is routinely used in hip fracture patients without any identified increased risks or complications, but there is a paucity of data on this subject, which is the rationale for this study.

We hypothesize that in patients with osteoporotic fragility fractures of the hip, patients receiving intraoperative long-acting local anesthetics will have decreased pain and decreased post-operative opiate requirements, leading to less delirium and decreased hospital resource utilization during their index hospitalization.

5. Inclusion and Exclusion Criteria

Inclusion Criteria

- Age 55 or older
- Sustaining either an OTA/AO type 31A or 31B fracture undergoing ORIF or hemiarthroplasty
- Able to consent
- Isolated injury

Exclusion Criteria

- OTA/AO 31B1 (Impacted/slightly displaced)
- Baseline dementia or cognitive deficit
- Inability to consent

- Chronic Opioid use
- End stage liver disease with Model for End-Stage Liver Disease (MELD) greater than 20.

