- **Primary Outcome Variables:** Total morphine equivalents in the post-operative period for 24, 48, and 72 hours, CAM score and average Pain Visual Analog Scale
- **Secondary Outcome Variables:** Length of stay, discharge disposition, timing and participation with inpatient physical therapy, complications and 30 day readmission.

10. Procedures Involved

- **Patient identification:** Patients will be identified on morning intake rounds by the trauma team and the research staff who are present daily to screen and enroll patients.
- **Screening/Enrollment:** The research staff will review the charts to identify patients meeting the inclusion/exclusion criteria. Patients will be approached for study participation and enrolled in the study prior to surgery. For potential participants, the research staff will interview the patients, confirm willingness to participate and inclusion/criteria.
 - We will utilize a Mini-COG (Screening for Cognitive Impairment in Older Adults)²⁷. A score of <4, which has been shown to have high sensitivity for dementia screening will define cognitive impairment and will preclude enrollment.
 - At time of enrollment, preoperative demographics will be recorded which will include age, sex, comorbidities, current use of anti-epileptic/anti-depressive medications for pain control, type of surgical approach, pre-ambulatory status and implant class.
 - After this review and screening, the patient will be given the opportunity to ask researchers questions about the study. It will be reiterated to all patients during preoperative discussions that their enrollment status in no way will affect their ability to get adequate post-operative pain control.
- **Randomization:** Randomization will be done through the research pharmacy. Participants will undergo block randomization (block size: 10) through a computer-generated algorithm.

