- Adverse events will be monitored and recorded during hospitalization following standard of care regiment and later be used and accessed for data collection of the research study. The adverse events monitored and recorded will include: alteration of mental status, respiratory depression, wound complications, fixation-related complications.
- The following information will be accessed via the electronic medical record after discharge:
 - Total morphine equivalents post-surgery, including and excluding recovery unit administration of narcotics in the immediate post-operative period.
 - Pain Visual Analog Score (VAS) score, which is obtained Q4 by nursing staff.
 - Timing and participation with physical therapy will be recorded looking at time until first therapy evaluation, and level of mobilization achieved
 - Length of stay, discharge disposition
- **Post-hospital follow-up:** Follow up after discharge will be done according to each individual surgeon's practice per their standard of care. It typically involves a follow up appointment at 2-4 weeks post-operatively, with longer follow-up as needed based on the injury type, surgical fixation strategy, and the trajectory of recovery. In addition to data collected as indicated above, including total morphine equivalents post-op period, CAM score, average pain VAS, length of stay, discharge disposition, timing/participation with inpatient physical therapy and adverse complications, data concerning 30-day patient readmission will be collected during the 30-day post-op period.

11. Data and Specimen Banking

No specimens will be obtained or retained for future study. The stored deidentified data from the study will be kept for a minimum of 6 years for records in the event follow-up studies are pursued and will remain protected and encrypted. Data will be permanently deleted following this time period. The banked data will be stored on a password-protected research drive corresponding to "orthotrauma (\\ummcnas03)". Upon conclusion of the study, the data will be stored in a password encrypted file that only the PI has access to.

12. Data Management

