Official Title: Does the Use of Liposomal Bupivacaine Decrease Narcotic Requirements in Geriatric Hip Fractures? A Randomized, Double Blinded Control Trial

NCT Number: NCT03289858

Date of Document: August 27, 2017

Statistical Analysis Plan for Randomized Controlled Trial for Exparel Hip Fracture (H00013594)

Primary Outcome Variables: Total morphine equivalents in the post-operative period for 24, 48, and 72 hours, CAM score and average Pain Visual Analog Scale

Secondary Outcome Variables: Length of stay, discharge disposition, timing and participation with inpatient physical therapy, complications and 30 day readmission.

Comparisons between continuous variables will be made using Students t-test, and categorical variables using the Chi-square statistic or Fischer's Exact Test, based on incidence.

Power analysis: Recent studies evaluating regional nerve blocks in hip fractures have shown an average morphine sulfate equivalent of 3.5 +/- 0.52 mg/d in the first 3 postoperative days. That same study showed a 33% reduction in morphine equivalents (3.5 mg/d vs 2.1 mg/d). Assuming a similar effect size, this study would require only 8 patients group to be powered to 80% with a significance level of 0.05. With a target recruitment goal of 50 patients, the study would be powered to detect differences as low as 0.42 mg/d (a 12% effect size)

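### Discharge disposition is a secondary outcome, but pre-fracture residence is not a listed baseline item, so return to a prior facility cannot be told apart from new institutionalisation

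*Protocol*

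**What the plan says.** Protocol section 9 lists the secondary outcomes as "Length of stay, discharge disposition, timing and participation with inpatient physical therapy, complications and 30 day readmission", and the SAP repeats the list. Section 10 says that disposition will be read from the electronic record once the patient has left hospital. Neither document gives categories for disposition or relates it to where the patient lived before.

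The enrolment data in section 10 are "age, sex, comorbidities, current use of anti-epileptic/anti-depressive medications for pain control, type of surgical approach, pre-ambulatory status and implant class". Pre-fracture residence, living situation and source of admission are not among them. The nearest item, pre-injury ambulatory status, concerns mobility.

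Section 5 does not exclude people who live in a facility. It does exclude "Baseline dementia or cognitive deficit" and inability to consent, and section 10 adds a Mini-COG threshold.

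On allocation, section 10 says: "Participants will undergo block randomization (block size: 10) through a computer-generated algorithm". No stratification is stated. For analysis, the SAP compares "categorical variables using the Chi-square statistic or Fischer's Exact Test, based on incidence", with no covariate or stratum.

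**The concern.** For a patient who already lives in a nursing or assisted-living facility, the discharge destination is likely to be largely settled before surgery. For a patient who lived at home, discharge to a facility is a change. The planned data hold both as the same kind of destination, with no field to separate them.

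A reader of the disposition table could not say how many facility discharges were simply returns to the previous residence. A treatment difference among home-dwellers would be diluted by patients whose destination hardly responds to treatment. In a trial of 60, a chance imbalance of a few facility residents could also widen or narrow the observed difference, and no baseline item would reveal it.

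**Working it through.** The documents state no figure for disposition, so there is none to reproduce. They also give no disposition rates and no share of facility residents. Every rate below is therefore an assumption. The only input from the documents is the recruitment goal of 60 (Protocol section 6), taken as 30 per arm; 1:1 allocation is itself assumed.

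**Assumptions.** Share of facility residents f = 5%, 10% or 20%. Among home-dwellers, discharge home is 35% in one arm and 65% in the other. The rest are split equally between rehabilitation and facility in the 65% arm (17.5% each), and 30% and 35% in the 35% arm. In both arms 90% of facility residents return to a facility.

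**Dilution.** If facility residents fare the same in both arms, the observed difference in home discharge is (1 − f) × (65 − 35) points: 0.95 × 30 = 28.5, 0.90 × 30 = 27.0 and 0.80 × 30 = 24.0 points.

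**Chance imbalance.** The number of facility residents in each arm is binomial(30, f), with mean 30f = 1.5, 3 or 6. Summing the joint probabilities over all pairs that differ by at least 3 gives 0.131, 0.275 and 0.417. With 25 per arm (the 50 used in the plan's power statement) it is 0.099, 0.231 and 0.374.

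**What an imbalance of 3 does.** If facility residents are taken never to go home, replacing three home-dwellers with three facility residents lowers an arm's expected home-discharge rate by 3 × 0.35/30 = 3.5 points or 3 × 0.65/30 = 6.5 points. The standard error of the difference between arms is about √(2 × 0.35 × 0.65/30) = 12.3 points. The shift is visible, but smaller than ordinary sampling error.

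**Power**, simulated with 4,000 trials per scenario, two-sided 5%:

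| Analysis | f = 5% | f = 10% | f = 20% |
|---|---|---|---|
| Chi-square, three assumed categories | 50.1% | 45.7% | 39.0% |
| Home yes/no, unadjusted | 61.3% | 56.7% | 47.8% |
| Return to prior residence, stratified Cochran-Mantel-Haenszel | 63.0% | 59.0% | 52.4% |

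The gain from the first row to the third is 12.9, 13.3 and 13.4 points. Of this, 11.2, 11.0 and 8.8 points come from reducing three categories to two, which needs no residence field. Recording residence accounts for the step from the second row to the third: 1.7, 2.3 and 4.6 points. A repeat with 8,000 trials per scenario gave 0.9, 2.3 and 4.1 points. With no treatment effect, rejection was 4.6–5.8% for the chi-square test and 4.1–5.3% for the stratified test, so both hold their level.

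**The case against.** Several stronger readings are tempting, and the documents do not support them.

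- **That a returning resident is scored as a poor result.** No scoring rule is written. The text supports only that the two kinds of patient cannot be separated.
- **That disposition is the outcome meant to show functional benefit.** The three aims in Protocol section 3 concern opioids and pain, delirium, and cost. None names disposition or independence.
- **That the gap cannot be repaired later.** The baseline list is introduced with "At time of enrollment, preoperative demographics will be recorded which will include age, sex, comorbidities" and is not expressly closed. Staff review charts and interview patients at enrolment, and prior residence may be in the record. But retrieval is not planned or assured. Section 12 limits what Kentucky shares to de-identified information on the endpoints and has identifiers destroyed after the secondary analysis. Section 27 limits record review to the orthopaedic injury and surgery.
- **That the comparison is biased.** Randomization balances residence in expectation, and the test's error rate already allows for chance imbalance.
- **That recording residence would raise power by about 13 points.** Most of that gain comes from merging categories, and the three categories are themselves an assumption.

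It is also fair to say that the cognitive exclusions probably lower the share of facility residents. At 5%, only 60 × 0.05 = 3 patients would be affected. The outcome is secondary and carries no power claim.

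All of this limits the size of the problem. It does not remove it: facility residence is not an exclusion, cognitively intact people also live in facilities, and neither site is committed to recording the field.

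**Conclusion.** The point holds as a low-cost improvement to one secondary outcome. As planned, return to a prior facility and new institutionalisation are indistinguishable, which leaves the comparison diluted, exposed to chance imbalance and difficult to interpret.

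In power terms the effect is small: about 1 to 5 points over a simple home yes/no comparison, for a facility share of 5–20% and the discharge rates assumed above. An imbalance of 3 or more facility residents has a 13% to 42% chance over the same range, and less if the cognitive exclusions bring the share below 5%. The stronger argument for acting is that the disposition table would otherwise not show who had lost their previous level of residence. Sample size and the primary outcomes are unaffected.

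**What to change.** - **Protocol section 10:** add pre-fracture residence to the enrolment data at both sites, recorded as home, assisted living or nursing facility. Three levels are needed. With only home and facility, an assisted-living resident discharged to a nursing facility would count as having returned.
- **Protocol section 12:** name this field among the data that Kentucky shares.
- **SAP:** define the disposition outcome as discharge to the pre-fracture level of residence or a more independent one (yes/no). State how rehabilitation discharge is classed for patients who came from a facility. Compare arms with a Cochran-Mantel-Haenszel test stratified by pre-fracture residence (home v facility), and show the raw disposition categories by arm descriptively.

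The cost is one extra chart field at enrolment and a few sentences across the protocol and SAP. The downside is that, for home-dwellers, rehabilitation and nursing-facility discharge are merged in the test; the descriptive table keeps them apart.

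### Walking status before the fracture is recorded but not used when mobilization in physical therapy is compared; the cost is precision in a secondary outcome, not validity

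*Protocol*

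**What the plan says.** Protocol Section 10 (Screening/Enrollment) lists "type of surgical approach, pre-ambulatory status and implant class" among the preoperative demographics. I read pre-ambulatory status as walking ability before the fracture; no scale is given.

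The same section, under data taken from the medical record, says physical therapy will be recorded "looking at time until first therapy evaluation, and level of mobilization achieved". No mobilization scale is given either.

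Section 9 and the SAP name the secondary outcomes: "Length of stay, discharge disposition, timing and participation with inpatient physical therapy, complications and 30 day readmission". Mobilization level is therefore a component of the physical therapy outcome, not a listed endpoint of its own.

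The SAP's whole method statement is: "Comparisons between continuous variables will be made using Students t-test, and categorical variables using the Chi-square statistic or Fischer's Exact Test, based on incidence". No model, covariate or stratum appears in either document. On allocation, Section 10 says: "Participants will undergo block randomization (block size: 10) through a computer-generated algorithm". No stratification factor is named.

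**The concern.** How far a patient mobilizes after hip fracture surgery plausibly depends on how well that patient walked beforehand. The eligibility criteria in Section 5 do not restrict walking ability, and Section 4 describes a frail population with several comorbidities, so the baseline spread may be wide. Neither the randomization nor the analysis uses a variable that is already in the dataset. Differences between patients then stay in the error term, and a chance imbalance between arms passes into the comparison uncorrected.

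A chi-square test on several mobilization levels also treats them as unordered labels, which discards information if the levels form a ladder.

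At stake is how sharply the trial can show whether better analgesia helps patients move. The primary outcomes and the stated sample size are not touched.

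**Working it through.** **Inputs.** From the SAP: 50 patients, SD 0.52 mg/d, and "powered to 80% with a significance level of 0.05". From protocol Section 6: 60 recruited, with 10-20% loss. Assumed: 1:1 allocation (25 per arm evaluable), two-sided testing, and the correlation ρ between walking status and mobilization, which the documents do not give.

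**1. The plan's own figure.** No power figure exists for mobilization. The nearest is the detectable difference in morphine equivalents. A two-sample t-test with 25 per arm and 80% power detects d = 0.809 SD, and 0.809 × 0.52 = 0.42 mg/d, with 0.42 / 3.5 = 12%. The stated figure reproduces, so the same d is the reference below.

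**2. Gain on a continuous scale.** Adjustment multiplies the residual variance by (1 − ρ²). The detectable difference becomes 0.809 × √(1 − ρ²), and the equivalent unadjusted size is 25 / (1 − ρ²). Power is for a true effect of 0.809 SD, with 47 degrees of freedom.

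| Assumed ρ | Detectable difference (SD) | Power | Equivalent n per arm |
|---|---|---|---|
| 0 (unadjusted) | 0.81 | 80% | 25 |
| 0.2 | 0.79 | 81.5% | 26.0 |
| 0.3 | 0.77 | 83.5% | 27.5 |
| 0.4 | 0.74 | 86.3% | 29.8 |
| 0.5 | 0.70 | 89.9% | 33.3 |
| 0.6 | 0.65 | 93.8% | 39.1 |

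**3. Gain on an ordinal scale.** Mobilization will probably be a few ordered levels, so the table above is optimistic. Small simulations (300 to 1,000 runs, 25 per arm, different assumed cut-points) gave these gains from adding the covariate to a proportional-odds model:

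- Latent ρ 0.3: between 0 and about 3 points.
- Latent ρ 0.5: between about 2 and 7 points in most runs. One set of 600 runs gave 76.5% to 84.2%, a gain of 7.7, with a Monte Carlo standard error of about 1.6 points on each figure.

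One set of 1,000 runs (latent shift 0.85) also included the planned chi-square test:

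| Latent ρ | Chi-square | Proportional odds, unadjusted | Proportional odds, adjusted |
|---|---|---|---|
| 0.3 | 59% | 79% | 81% |
| 0.5 | 59% | 78% | 85% |

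Using the ordering adds 79 − 59 = 20 and 78 − 59 = 19 points. The covariate then adds 81 − 79 = 2 and 85 − 78 = 7.

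**4. Chance imbalance.** If half of the patients walked independently, an exact binomial calculation gives a 20% chance that the arms differ by 20 percentage points or more at 25 per arm, and 15.5% at 30 per arm. At 30% prevalence the figures are 16% and 12%. Take a split of 15/25 against 10/25 with ρ = 0.5. The walking indicator has an SD of about 0.5, so the shift is (0.20 / 0.5) × 0.5 = 0.2 SD in favour of the better-walking arm. Given that split and no drug effect, simulation puts false positives in that direction at 6.9% instead of 2.5%.

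**5. Discharge disposition.** Binary outcome (home or not), 25 per arm, 60% independent walkers, odds ratio 4, unadjusted chi-square against a Mantel-Haenszel test stratified by walking status. All rates are assumed.

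| Home discharge in controls, walkers vs non-walkers | Unadjusted | Stratified |
|---|---|---|
| 50% vs 10% | 51% | 55% |
| 60% vs 20% | 55% | 56% |
| 40% vs 30% | 70% | 65% |

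Without a treatment effect the unadjusted test rejected slightly too often (5.6-6.3%, against 4.9-5.1% stratified), so part of the apparent loss in the last row reflects test size.

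**The case against.** The strongest reply is that nothing here is an error. Randomization makes the unadjusted test valid, and its 5% error rate already averages over chance imbalances. Walking status is listed with the demographics, where describing the cohort is reason enough to record it; the documents never say it was meant as a covariate. The outcome is secondary and unpowered. Eligible patients are cognitively intact with an isolated injury, which may narrow the range of walking ability and lower ρ. All of this stands, and it limits the point to an inexpensive improvement.

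A reader might go further and infer that the comparison is biased, or that an imbalance would be mistaken for a drug effect. The documents do not support that: the 6.9% in step 4 is conditional on one unfavourable split, and over all allocations the error rate stays nominal. A reader might also expect a similar gain for discharge disposition; step 5 shows a modest gain or none.

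It is also fair to object that the continuous-scale figures model neither the planned test nor a coarse scale. Step 3 answers this, and shows that ordinal modelling, not the covariate, brings most of the improvement.

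The objection does not remove the main point. The baseline is collected and the analysis text makes no use of it. If an imbalance appeared after unblinding, an adjustment chosen then would be post hoc and less credible.

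**Conclusion.** The point holds as a low-cost improvement to the analysis of one secondary outcome. As written, the SAP would compare a categorical mobilization outcome without its recorded baseline and without any ordering of its levels. The test is valid; precision and protection against chance imbalance are what is lost.

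The size is uncertain. On a continuous scale the covariate is worth about 4, 6 or 10 points of power at ρ of 0.3, 0.4 or 0.5; on a coarse ordinal scale, about 0 to 7 points at 0.3 to 0.5. At ρ of 0.3 or below the gain is small either way. These figures rest on an assumed ρ, 25 per arm, two-sided 5% testing and, for the ordinal case, assumed cut-points. If mobilization were instead scored numerically, the SAP's t-test would apply, the ordering argument would fall away, and the continuous-scale figures would be the relevant ones.

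**What to change.** Before unblinding, amend the SAP to:

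1. Define ordered categories for pre-ambulatory status and for mobilization level, since neither has a scale now.
2. Compare mobilization by a proportional-odds model with treatment and pre-ambulatory status, the latter as one linear term or very few categories given 50-60 patients.
3. Keep the chi-square or Fisher test as an unadjusted sensitivity analysis.
4. Report pre-ambulatory status by arm.

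Adjusting discharge disposition for the same variable can be left optional.

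The cost is SAP wording, 1-2 degrees of freedom, a conditional odds ratio that is harder to explain than a difference in percentages, and statistical software other than the spreadsheets named in protocol Section 12. No new variable, visit, procedure or patient is needed.
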